Context: Unresolved psychological problems, such as anxiety, affect a significant number of our students and interfere with their ability to attend, actively participate, and prosper in school. This project will expand the capacity of selected mental health agencies to provide services in the participating schools through school therapeutic services (STS). The project will provide enhanced training in evidence-based behavioral health interventions to school-based mental health providers. The services will be implemented by STS Master's level therapists supervised by their mental health agency supervisors (Internal Support), who are in turn supported by the research team (TT) or external consultants (TT+).

Objectives: The purpose of this intervention study is to test the effectiveness of FRIENDS (a program for overanxious children) compared to an adapted version (CATS) and to compare the total cost between the interventions. The study also aims to compare support mechanisms: Train-the-Trainer (TT) to Train-the-Trainer Plus (TT+) for the implementation of CATS and to test mediators and moderators of type of support (TT vs. TT+) on therapist fidelity.

Study Design: This is a 3-arm, parallel group, Type 2 hybrid effectiveness-implementation trial in K-8 schools in Philadelphia over 5 years.

Setting/Participants: Schools within the School District of Philadelphia that have STS programs managed by mental health agencies are potentially eligible for participation. Schools (3-6 per agency) will be chosen for participation. Students who present excessive anxiety in grades 4-8 would be potentially eligible to participate in the interventions offered by the agencies' therapists in their school.

Study Interventions and Measures:

This study is designed to test: a) the effectiveness of an adapted version of a group cognitive behavioral therapy program (CATS) compared to the original version of this program (FRIENDS), and b) the effectiveness of two implementation strategies for CATS: Train-the-Trainer and Train-the-Trainer Plus. CATS is a shorter, more culturally sensitive, focused, and feasible CBT for anxiety in children than FRIENDS. CATS addresses one of the major barriers to implementation (intervention-context fit).

Therapists and supervisors will be randomly assigned to one of three conditions: a) FRIENDS with Train-the-Trainer implementation strategy (i.e., Masters-level supervisors receive training by experts on conducting supervision); b) CATS with Train-the-Trainer strategy; c) CATS using the Train-the-Trainer Plus strategy (i.e., supervisors receive training and consultation by experts on conducting supervision). Effectiveness will be measured by comparing A to B; Implementation will be measured by comparing B to C. Agency therapists will conduct all treatment groups in the schools.

1 BACKGROUND INFORMATION AND RATIONALE

1.1 Introduction

Unmet need for mental health services remains extraordinarily high, especially among urban low-income children. Anxiety disorders in particular are highly prevalent among children in low-income, high-stress communities, and have been linked to academic and social problems and emotional maladjustment later in life. Schools in low-income urban communities present a context with great potential for implementation of psychosocial EBPs. Cognitive-behavioral therapy (CBT) is an EBP that has been found to be very effective in treating anxiety in various settings, including schools. Friends for Life (FRIENDS) is an efficacious group CBT protocol for anxiety. Unfortunately, CBT for anxiety is seldom employed in under-resourced urban schools, mainly because the treatment protocols are not tailored for the context or the population, existing behavioral health staff do not receive adequate training or support to allow them to implement the treatment with fidelity, and school districts do not have the resources to contract outside providers or consultants. Community Behavioral Health (CBH), a non-profit organization that manages Medicaid funds for the City of Philadelphia, has approached us for help to develop costeffective implementation strategies for schools. The availability of a contextually relevant, feasible, and cost-effective evidence-based CBT protocol for urban schools designed to be implemented and supported by existing agencies would address existing gaps in services for children who might otherwise go without treatment.

1.2 Name and Description of Investigational Product or Intervention

1.2.1 Interventions implemented for anxious students by city agency therapists:

Friends for Life (FRIENDS): FRIENDS, a GCBT program, is an effective program for the prevention and treatment of anxiety disorders in children evidenced by a meta-analysis on school-based interventions for at-risk and clinically anxious youth. FRIENDS has been successfully implemented in several countries with children from diverse ethnic backgrounds. FRIENDS was developed based on the view that anxiety is a tripartite construct involving physiological, cognitive, and behavioral components.

Core components: Experts in CBT for childhood anxiety disorders have identified 5 essential components: psychoeducation, somatic management skills training, cognitive restructuring, exposure methods, and contingency management. The FRIENDS protocol consists of 10 weekly sessions and two booster sessions. We included the booster sessions in the regular protocol for a total of 12 sessions.

Adapted CBT for Anxiety Treatment in Schools (CATS): We conducted planned adaptations to the FRIENDS protocol based on our collective experience with the protocol and qualitative data (focus group and interviews). We followed procedures developed by Lee and colleagues, including surveying service providers and trainers regarding the appropriateness of FRIENDS for the target population. Changes were made to the language (idioms, metaphors, words), cultural fit (cultural values), methods (session length, number of sessions), activities (in-session practices), which resulted in additions and substitutions in these areas while maintaining the 5 essential components of the treatment. CATS is a briefer (8-session) and more engaging and culturally-sensitive protocol than FRIENDS.

1.2.2 Support Interventions (strategies) offered to city agency therapists implementing CATS

Train the Trainer (TT) by which agency supervisors are trained to conduct effective supervision, and then go on to train therapists.

Train the Trainer Plus (TT+) a modified train-the-trainer approach by which supervisors receive training plus extended consultation on conducting effective supervision.

1.3 Findings from Non-Clinical and Clinical Studies

We pilot-tested FRIENDS with low-income urban children who were at risk or who met diagnostic criteria for an anxiety disorder. The treatment was part of a school-wide positive behavioral interventions and supports (SWPBIS) program (CDC, R18MN000003) in 2 K-8 public schools in Philadelphia. The development and implementation of these programs was based on the Public Health Approach. The proposed project will take place in similar schools. We interviewed the parents of 111 randomly selected children in order to assess mental health characteristics of the typical student attending the participating schools. On the Child Behavior Checklist, 28% of the children were rated within the borderline range or higher (T score > 60) on the Anxious/Depressed subscale and 9% were rated within the clinical range (T score > 70). The corresponding percentages for externalizing disorders were 29%, and 17%, respectively, indicating that the number of children at risk for anxiety is very similar to the number of children at risk for externalizing disorders.

Six graduate students in applied psychology and three counselors from each school were trained in and co led FRIENDS groups. The fidelity scores reflected the ability of graduate students and school counselors to implement the interventions with fidelity while receiving expert support. Six FRIENDS groups were conducted. All of the sessions were video recorded to assess content fidelity. Fidelity ratings were obtained from an independent coder (IC). Average fidelity to the FRIENDS manual across sessions and groups was 86%, considered moderate to strong fidelity. Of the 33 children who participated, only 10 (30%) children participated in all 12 sessions. Although only 30% of participants attended all originally scheduled sessions, 85% of participants received the entire content of the intervention. The procedure was for school counselors and project staff to review material with absent participants individually, or in groups of two, prior to the upcoming session. Following this procedure, 85% received all session content.

The findings from the pilot study are relevant for the proposed study because they show that: a) the prevalence of anxiety problems in the schools where the proposed project would take place is high; b) less than a third of the children participated in all 12 session, indicating that a briefer protocol would be more feasible in urban schools; c) counselors functioning as co-therapists with graduate students can deliver FRIENDS with relatively high levels of fidelity; and (d) the treatment led to reductions in diagnostic level and symptom severity.

Furthermore, in preparation for this project, we conducted qualitative interviews with 5 consultants from our current SWPBIS project (R01HD073430) and focus groups with school counselors implementing FRIENDS. A qualitative theme analysis (i.e., frequency of themes) about consultants' perceptions regarding context-fit of FRIENDS revealed that the protocol is too long, uses language and examples that are not congruent with the language and culture of low income, ethnically diverse children, and does not sufficiently emphasize teaching relaxation and exposure. Counselors thought the manual is "dry" and "boring" and

that it needs to be "tweaked" in order to increase children's engagement. Counselors requested more optional activities to support main ideas in the manual.

1.4 Relevant Literature and Data

Anxiety disorders (i.e., Generalized Anxiety Disorder, Social Phobia, Specific Phobia and Separation Anxiety Disorder), affect up to 13% of the child population making them among the most common childhood conditions. Anxiety disorders are highly prevalent among inner city school children and often go unidentified and untreated. Children with these disorders are more likely than their peers to have problems with social, peer and parent-child relations, academic achievement school refusal and future socio-emotional adjustment. School factors, such as peer problems, academic pressures, and school violence, can contribute to and exacerbate symptoms.

Individual and group CBT (GCBT) have been shown to be highly effective for the treatment of anxiety in youth. GCBT requires fewer resources than individual CBT, such as one therapist treating several children at once, thus making it less expensive for use in underresourced settings such as urban schools. GCBT for anxiety has successfully been employed in urban school settings by our team and others. FRIENDS, a GCBT program, is an effective program for the prevention and treatment of anxiety disorders in children as evidenced by a meta-analysis on school-based interventions for at-risk and clinically anxious youth. Also, our previous research demonstrates that FRIENDS is an effective protocol for use in urban public schools.

Public schools have become a common setting for the delivery of mental health services to children and may be the ideal context through which to narrow services disparities. The school is a convenient location where services can often be provided at little or no cost to families. Benefits of providing EBPs in schools include the ability to implement interventions in the very environment in which most symptoms are triggered and to incorporate protocol-specific interventions, with peer and teacher involvement, as needed for generalizability. EBPs for anxiety disorders enable overanxious children to overcome behavioral barriers to learning.

The most pressing challenge facing the mental health field is the dissemination and implementation (D&I) of EBPs: taking protocols that were developed in research settings and adapting them for specific community use. It has been estimated that it can take up to 17 years for new EBPs to make their way from research to practice. The delay is likely longer for child treatments in urban settings. The customary step-wise progression from clinical efficacy to clinical effectiveness in practice to implementation contributes to the long delay between the development of a treatment and its routine implementation in a community setting. Curran and colleagues have proposed three hybrid designs to galvanize the translation of efficacious treatments to enhance their public health impact. These research designs are thought to facilitate "more rapid translational gains, more effective implementation strategies and [yield] more useful information for decision makers. In the Type II design, effectiveness and implementation have equal importance. Type II effectiveness-implementation hybrid studies are most appropriate for treatments that have a strong record of efficacy and effectiveness, such as FRIENDS.

Treatments that are developed and tested for efficacy in highly controlled research settings often do not fit into "real world" contexts. As a result most effective treatments in health and mental health settings need to be adapted for new contexts. Unfortunately, in the adaptation process, there is a potential for some of the main components of the treatments to be altered, rendering them less effective than in their original form. Lee and colleagues developed planned adaptation (PA) to address the tension between "implementing"

programs with fidelity and the need to tailor programs to fit the target population". PA orients the provider to the program and its theoretical orientation. A central tenet of PA is that adaptation must be conducted without altering the program's core components. PA helps the provider identify components of the program that can be modified, and provides a process for conducting adaptations and a direction on how to develop evaluation strategies. We applied PA to FRIENDS in order to make it more feasible for implementation in colocation settings with low-income urban children.

Substantial resources have been dedicated to the D&I of mental health EBPs. Key to that effort has been the identification of strategies for training community-based clinicians. Studies have shown that effective training models include initial workshops for therapists that are followed up with supervision, which often includes coaching and performance feedback. This was the strategy employed by our research team for an R01 study testing the effectiveness of consultation only vs. consultation plus coaching in the implementation of an EBP in public schools in the SDP. Another important challenge facing publicly funded mental health agencies is finding cost-effective strategies for supporting supervisors. Most community mental health agencies, where low-income urban children receive services, do not have the resources to pay for ongoing expert direct consultation for therapists who implement EBPs. As such, finding time- and cost-effective alternative strategies for supporting therapists would have a significant public health impact. An important feasibility question is, "Can internal clinical supervisors who are not familiar with EBPs provide effective supervision to therapists after participating in training workshops or do they need more extensive support?" A mostly self-sustaining system as previously described would likely be more practical and less expensive but perhaps lead to fewer positive child outcomes compared to a system where supervisors are provided extended consultation. Two alternative, and potentially cost effective, strategies are the cascade or train-the-trainer (TT) approach, by which agency supervisors are trained to conduct effective supervision, and then go on to train therapists; and a modified train-the-trainer approach by which supervisors receive training plus extended consultation (TT+) on conducting effective supervision. TT has been used with adult mental health populations. Two pilot studies using this approach have reported improved therapist knowledge and improved client behavior, but it is not known whether these findings could generalize to other settings or populations. TT+ has been used by Bruce Chorpita and colleagues with agency supervisors who support therapists in the implementation of modular individual CBT. Highlights of this approach include initial training, biweekly or monthly phone consultations with supervisors and a supervisor promotion review. This modified train-the-trainer approach has been found to lead to moderate outcome effect sizes.

This current study has the potential to demonstrate that agency therapists and supervisors who have had little to no prior exposure to EBPs can implement an anxiety disorders EBP with fidelity. The use of group therapy can contribute to lowering services disparities in urban schools. Comparisons of the two implementation strategies (internal supervision with or without consultation for supervisors) would provide large urban mental health systems with data to make decisions about adoption of EBPs. The study is consistent with the goals of the Affordable Care Act in that it would generate information on implementation of effective practices that optimize delivery of mental health care to traditionally underserved communities.

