6.1 Primary Endpoint

Effectiveness between treatment groups (FRIENDS and CATS) will be tested by calculating the 95% confidence limits (the width of the limit =|4.20|) for the differences in symptom severity, impairment, and academic competence (child outcomes) from pre to post between children receiving FRIENDS and children receiving CATS. If the calculated differences are within the 95% limit, then we will conclude that the two interventions have an equal impact or effect on child outcomes. If any of the differences in child outcomes is/are larger than the upper limit, then we will conclude that one intervention is better than the other. The limit of |4.20| was chosen based on the distribution of the reported mean effect sizes associate with FRIENDS.

Qualitative interviews with supervisors and therapists (perceived acceptability of support strategies) will be audio-recorded, transcribed and entered into NVivo 10.0 for coding and analysis. For each interview, a codebook (of common themes related to the appropriateness and acceptability of the support they received) will be developed and trialed by three coders based on an initial reading of the transcripts, and revised through discussions and subsequent transcript reviews. Coders will meet regularly to compare coding and revise the codebook. This will yield a stable set of qualitative codes that will be used to code the transcripts. Two independent coders will then code all of the transcripts. This iterative process will be continued until consensus is reached and saturation occurs. Coder reliability will be checked quarterly using the inter-rater reliability function in NVivo.

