6.3 Sample Size and Power

Number of students and statistical power. It is anticipated that a total of 284 (142 students per treatment protocol) will complete the proposed study. The published reported effect size of FRIENDS has been estimated to equal 0.56 (cohen's *d*). In testing for equivalence of FRIENDS and CATS, using two one-sided tests with sample sizes of 142 in FRIENDS and 142 in CATS achieves 88% power at a 5% significance level when the true difference between the means is 0 (null hypothesis), the standard deviation of the differences in means is assumed to be 11, and the equivalence limits are -4.20 and 4.20.

Number of therapist and statistical power. To compare TT to TT+ for the implementation of CATS (H2a), with 30 therapists in TT and 30 in TT+ achieve 86% power to detect a

difference of 8% between the null hypothesis that both group means are 80% (content fidelity) and the alternative hypothesis that the mean of group TT is 80% with estimated group standard deviations of 10 and 10 (an estimated effect size=.8) and with a significance level (alpha) of 0.05 using a two-sided two-sample t-test. Similarly, group sample sizes of 30 and 30 achieve 84% power to detect a difference of 0.7 in process fidelity between the null hypothesis that both group means are 4 and the alternative hypothesis that the mean of group TT+ is 4.7 with estimated groups standard deviations of 0.9 and 0.9 (an estimated ES= .78) and with a significance level (alpha) of 0.05 using a two-sided two-sample t-test.

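### Sections 6.1 and 6.3 allow only 'equal' or 'one intervention is better' for FRIENDS versus CATS; no conclusion is attached to CATS being not worse by the margin, and the rule handles a moderate CATS advantage or loss poorly

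*Combined protocol and SAP*

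**What the plan says.** **Rationale.** Section 1.4 says that adapting a treatment carries a risk of "some of the main components of the treatments to be altered, rendering them less effective than in their original form". This is a remark about adaptation in general, and the section goes on to planned adaptation of FRIENDS. The abstract gives the attraction of the new version: "CATS is a shorter, more culturally sensitive, focused, and feasible CBT for anxiety in children than FRIENDS". Section 1.2.1 adds that it has 8 sessions, against 12 for FRIENDS as delivered here.

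**Objective.** The abstract and section 2.1 ask only for a comparison of the two treatments. Neither specifies equivalence, non-inferiority or superiority.

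**Sizing.** Section 6.3 uses an equivalence design: "using two one-sided tests with sample sizes of 142 in FRIENDS and 142 in CATS achieves 88% power at a 5% significance level". The power is given only for the case "when the true difference between the means is 0", with SD 11 and limits of ±4.20.

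**Decision rule.** Section 6.1 has two branches. Differences inside the limit mean an equal effect. The other branch reads: "If any of the differences in child outcomes is/are larger than the upper limit, then we will conclude that one intervention is better". It names no direction, does not say whether the observed difference or its confidence interval is compared with 4.20, and covers several child outcomes together. Section 6.1 refers to 95% limits.

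**The concern.** A system choosing between 12 and 8 sessions needs to know first whether the shorter programme loses a relevant amount of effect. That is a one-sided question, and one of the two one-sided tests in 6.3 answers it. The plan attaches no conclusion to that test alone, and it plans no test against zero. If CATS is somewhat better than FRIENDS, the upper equivalence limit counts against it, while the advantage may be too small for the 'better' branch. If CATS is somewhat worse and the rule uses the observed difference, the loss can be labelled 'equal'. At stake is whether the main effectiveness comparison gives a usable and correctly directed answer when the truth is not exactly zero.

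**Working it through.** **Inputs (section 6.3):** 142 per arm, SD 11, limits ±4.20, 5% level. The SD is read as the per-student SD, because that reading reproduces the stated power. Children are treated as independent, as in the plan.

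SE = 11 × √(2/142) = 1.305.

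**1. The plan's own figure.** Each one-sided test at 5% and a true difference of 0: Φ(4.20/1.305 − 1.645) = Φ(1.572) = 0.942. Power for both tests: 2 × 0.942 − 1 = 0.884 (0.882 with the t distribution). The stated 88% is reproduced. It corresponds to a two-sided 90% interval inside ±4.20. With a 95% interval, as 6.1 suggests, the power is 79% (0.787, t-based).

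**2. Non-inferiority alone, true difference 0.** 94% at one-sided 5% (the 0.942 above). At one-sided 2.5%, Φ(3.217 − 1.960) = 0.896 by the normal approximation and about 89% with the t distribution.

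**3. CATS truly better by 3 points (0.27 SD).** The documents state no expected advantage, so this value is an assumption.

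- Equivalence (both one-sided tests): 0.233.
- Observed difference above 4.20: 1 − Φ((4.20 − 3)/1.305) = 0.179.
- Whole 95% interval above 4.20: the observed difference must exceed 4.20 + 1.96 × 1.305 = 6.76, probability 0.002.
- Not worse by 4.20: Φ((4.20 + 3)/1.305 − 1.645) = Φ(3.87), about 100%.
- Ordinary superiority (95% lower limit above 0): Φ(3/1.305 − 1.96) = 0.632.

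| Reading of 6.1 | Equal | One is better | No conclusion |
|---|---|---|---|
| A. Observed difference against ±4.20 for both branches | 82% | 18% | 0% |
| B. Two one-sided tests for 'equal', observed difference for 'better' | 23% | 18% | 59% |
| C. Two one-sided tests for 'equal', whole 95% interval beyond 4.20 for 'better' | 23% | 0.2% | 1 − 0.233 − 0.002 = 76.5%, about 77% |

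**4. Reading A under a loss.** If CATS is truly worse by exactly 4.20, the observed difference falls inside the limit about half the time, so about 50% of such trials would be called equal.

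**5. Other true advantages.**

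| CATS better by | Equivalence | No conclusion, reading B | Not worse by 4.20 (one-sided 5%) |
|---|---|---|---|
| 1 | 78% | 21% | 99% |
| 2 | 51% | 44% | 99.9% |
| 2.5 | 37% | 54% | about 100% |
| 3 | 23% | 59% | about 100% |
| 4 | 7% | 49% | about 100% |
| 5 | 1% | 26% | about 100% |

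The chance of concluding equivalence falls below one half once the true advantage exceeds 4.20 − 1.65 × 1.305, about 2.05 points (0.19 SD).

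**The case against.** A reader might infer that the comparison is decided only by the equivalence test. It is not: 6.1 has a 'better' branch, and by 5 points under reading B that branch is the likely result (73%).

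A reader might also infer that a moderately better CATS would usually end with no conclusion. The documents do not support that in general. Under reading A there is always a conclusion. Under reading B no conclusion is the majority result only from about 2.3 to just under 4 points, and at 1 point equivalence still succeeds 78% of the time. Only reading C makes it the most likely result over a wide range, from about 2.05 to 6.8 points.

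Nor is the protocol's concern purely one-directional. The remark in 1.4 is general, 1.2.1 says the five essential components were kept, and 1.3 gives reasons why CATS may fit better. No section predicts an advantage of a given size.

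Equivalence is also a defensible choice. Section 2.1 is neutral, cost is compared alongside effect, and a reader of the planned interval could compare its lower limit with −4.20 unaided. At a true difference of 0 the power gain is small: 89% at one-sided 2.5% against 88%.

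These points limit the claim. They do not supply the missing conclusion, and they do not settle which reading of 6.1 applies.

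**Conclusion.** The point holds in a limited form. Sections 6.1 and 6.3 give no way to conclude that CATS is not worse by the margin, or that it is better by less than 4.20. At an assumed 3-point advantage, the three readings give 82% 'equal', 59% no conclusion and about 77% no conclusion, while the one-sided test already contained in 6.3 would succeed about 100% of the time. The observed-difference reading also gives weak protection against loss, since about 50% of true losses of exactly 4.20 would be called equal.

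This is not a reason to replace the equivalence design. It is a cheap improvement that should be made. The figures rest on SD 11, 142 per arm and independent children. Schools are randomised (8.1.1) and treatment is given in groups of 4 to 6 (3.2.2), so clustering would lower both the equivalence and the non-inferiority power.

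**What to change.** Before outcome data by arm are examined, rewrite the FRIENDS-CATS rule in 6.1 so that it uses the confidence interval and not the observed difference. For one named primary child outcome, with the difference defined as CATS improvement minus FRIENDS improvement:

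1. CATS is non-inferior if the lower limit of the two-sided 90% interval is above −4.20.
2. The programmes are equivalent if the upper limit of that interval is also below +4.20.
3. If CATS is non-inferior, report it as statistically better if the lower limit of the two-sided 95% interval is above 0, and say whether the difference exceeds 4.20.

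State the confidence level at each step, because 95% limits throughout would give 79% equivalence power and not 88%. Treat the other child outcomes as secondary, or adjust for multiplicity. In 6.3, report the non-inferiority power beside the equivalence power.

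**Cost.** Wording only, with no additional children. There are three downsides. The headline may be 'not worse' where 'equivalent' was hoped for. A result can be both equivalent and statistically better. Testing against 0 also raises the false 'better' rate at true equality, from about 0.1% under the observed-difference threshold (2 × [1 − Φ(3.217)]) to 2.5% for CATS, or about 5% if a mirror test for FRIENDS is added.
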